5.2 Phase II

Once dose escalation and de-escalation has completed with determination of the MTD/RP2D (**Phase I completed November 25, 2019**), the phase II portion of the study will begin. Patients will be enrolled to two cohorts, based on prior BTK inhibitor treatment: BTK-pretreated and BTK-naïve (**see below**). Patients will be treated until disease progression or until unacceptable toxicity, with dose modifications and delays as described in Section 6.5.

August 7, 2020: Phase II opened December 17, 2019 with Cohort A: BTK-naïve or Cohort B: BTK-pretreated.

Enrollment to Cohort A: BTK-naïve will continue. We plan to reach our original accrual goal of 36 BTK-naïve subjects treated at the established Dose Level 2 for 31 eligible, treated patients. The Phase I BTK-naïve patients treated at Dose Level 2 will be included in the 36 patient total. Seventeen additional BTK-naïve patients will be enrolled to complete this cohort.

Enrollment to Cohort B: BTK-pretreated will close. To date, only two patients have enrolled in Cohort B.

6. Treatment Plan

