12.1.2 Phase II

For the phase II portion of the study, we will accrue patients to two cohorts (BTK-naïve [Cohort A] and BTK-pretreated [Cohort B]) simultaneously. The primary endpoint for the phase II study will be the CR rate, with planned comparison to historical controls. The target CR rate for the BTK-naïve cohort will be 40%, based on a historical rate of 21% for single agent ibrutinib, and the target CR rate for the BTK-pretreated cohort will be 23% based on a single agent CR rate of 8% for bortezomib. As a result, we will accrue 31 eligible, treated patients to each cohort for a total of 62 eligible, treated patients for the phase II study. To assure an adequate number of eligible, treated patients, up to 36 patients will be enrolled to each arm.

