12.1.2.1 Administrative Changes: August 7, 2020

Due to administrative and/or industry sponsor reasons, it was decided that enrollment to Cohort B (BTK-pretreated cohort) will be stopped. The total number of BTK-pretreated patients enrolled was 2 as of August 7, 2020.

Enrollment to Cohort A (BTK-naïve cohort) will continue however, and up to the full accrual of 36 patients as initially planned. To supplement the enrollment of 36 patients in Cohort A, the BTK-naïve patients that were treated at the R2PD in Phase I (n=6) will contribute to the 36 patients needed for full accrual in Phase II.

The statistical operating characteristics, and primary endpoint, of the BTK-naïve cohort remains the same as indicated in Section 12.1.2 above.

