12.2 Phase II

12.2.1 Primary Objectives

Patients will receive oral ixazomib and ibrutinib, in combination, at the RP2D. The efficacy of ixazomib and ibrutinib therapy will be assessed using CR rate. The CR rate will be the defined as the percentage of patients who achieve a CR (confirmed by BM biopsy) within the first 12 months of initiating treatment. Patients who are unevaluable or whose CR is not confirmed by BM biopsy will be included in the denominator as non-responders when computing the CR rate. Relapse/progression will be defined as either frank progression by clinical or laboratory exam (i.e., increased circulating monoclonal lymphocytes) or progressive disease by restaging CT, defined according to standard criteria.³⁴ Patients with isolated lymphocytosis shall not constitute progression in the absence of other findings.

In order to facilitate rapid accrual and to determine evidence of efficacy in multiple clinical settings, patients in the phase II portion of the study will be divided into two cohorts. Cohort A will include BTK-naïve patients. Cohort B will include BTK-pretreated patients. **August 7, 2020: BTK-pretreated cohort closed.**

Based on a historical single-agent 21% CR rate of ibrutinib in relapsed/refractory MCL⁴, we would consider a CR rate of 40% for the combination therapy in the BTK-naïve cohort (Cohort A) to be of interest. To detect an improvement of CR rate to 40% from the historical CR rate of 21%, a total of 31 patients will be accrued to Cohort A. This design will have 86% power and 10% one-sided Type I error using an exact binomial test and the null hypothesis will be rejected if CR is observed in 10 or more patients.

For the BTK-pretreated cohort (Cohort B) a CR rate of 23% will be of interest and a CR rate of 8%, based on a previously reported single agent CR rate for bortezomib, will not be of interest. To detect an improvement in CR rate to 23% from 8%, a total of 31 patients will also be accrued to Cohort B. This design will have 87% power and

10% one-sided Type I error using an exact binomial test and the null hypothesis will be rejected if CR is observed in 5 or more patients. **August 7, 2020: BTK-pretreated cohort closed.**

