To assure an adequate number of eligible, treated patients, up to 36 patients will be enrolled to each arm. This will result in a maximum accrual of 84 patients for the full study (**August 7, 2020: BTK-pretreated cohort closed; updated per Section 12.1.2.1.**)

The efficacy assessment population will include all eligible and treated patients while the adverse events assessment population will include all treated patients, regardless of eligibility.

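### Cohort A's cut-off of 10 complete responses holds its 10% type I error only up to 31 patients, but up to 36 may be analysed

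*Protocol*

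**What the plan says.** Protocol 12.2.1 tests a CR rate of 40% against "a historical rate of 21% for single agent ibrutinib" (the wording of 12.1.2) in 31 Cohort A patients. It claims 86% power and 10% one-sided type I error from an exact binomial test. The same sentence gives the decision rule: "the null hypothesis will be rejected if CR is observed in 10 or more patients". The rule is a bare count and no sample size is attached to it.

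The number who will be analysed is described elsewhere:

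- Section 12.1.2 says that "up to 36 patients will be enrolled to each arm", so that enough are eligible and treated.
- Section 5.2 says "We plan to reach our original accrual goal of 36 BTK-naïve subjects treated at the established Dose Level 2 for 31 eligible, treated patients", and then "Seventeen additional BTK-naïve patients will be enrolled to complete this cohort".
- Section 12.1.2.1 says that the BTK-naïve Phase I patients treated at the recommended dose "will contribute to the 36 patients needed for full accrual in Phase II". It adds: "The statistical operating characteristics, and primary endpoint, of the BTK-naïve cohort remains the same as indicated in Section 12.1.2 above".
- Section 12.2.2 says "The efficacy assessment population will include all eligible and treated patients".
- Section 12.2.1 keeps unevaluable patients, and those with an unconfirmed CR, in the denominator as non-responders.

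No section limits the primary test to 31 patients or gives a cut-off for any other number.

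**The concern.** A cut-off on a count is valid only for the sample size it was derived from. Here the count is printed for 31, while accrual is managed to an enrolled total of 36. Only patients who are ineligible or never treated leave the denominator, so fewer than five such losses out of 36 puts the analysed number above 31. Section 12.2.2 itself works out safety precision for 36 treated patients, so the protocol contemplates all 36 being treated.

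At 32 or more, the sentence in 12.2.1 contains two rules that can disagree: the named exact test at 10%, and the count of 10. With Cohort B closed, this is the only efficacy decision rule still in use, and the comparison is with a historical rate. If the choice between count and test is made once the responses are known, the primary conclusion is chosen after the fact. The statement in 12.1.2.1 that the operating characteristics are unchanged holds only if exactly 31 are analysed.

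**Working it through.** **Inputs.** Null CR rate 0.21, alternative 0.40, planned n = 31, cut-off 10, one-sided 10%, exact binomial (12.1.2 and 12.2.1); maximum enrolment 36 (12.1.2, 12.1.2.1).

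**Formula.** P(X ≥ r | n, p) = Σ from x = r to n of C(n, x) p^x (1 − p)^(n − x). Type I error uses p = 0.21 and power uses p = 0.40.

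**The plan's own figure.** For n = 31, r = 10, type I error is 0.0975 and power is 0.8566. These match the stated 10% and 86%. With r = 9 the type I error would be 0.1871, so 10 is the correct cut-off at 31.

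**The same formula at other n.** The exact cut-off is the smallest r with type I error at or below 10%.

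| n | Count of 10: type I error | Count of 10: power | Exact cut-off | Its type I error | Its power |
|---|---|---|---|---|---|
| 28 | 5.3% | 74.1% | 10 | 5.3% | 74.1% |
| 29 | 6.6% | 78.5% | 10 | 6.6% | 78.5% |
| 30 | 8.1% | 82.4% | 10 | 8.1% | 82.4% |
| 31 | 9.8% | 85.7% | 10 | 9.8% | 85.7% |
| 32 | 11.6% | 88.4% | 11 | 5.6% | 79.5% |
| 33 | 13.7% | 90.8% | 11 | 6.9% | 83.1% |
| 34 | 15.9% | 92.7% | 11 | 8.3% | 86.2% |
| 35 | 18.4% | 94.2% | 11 | 9.9% | 88.8% |
| 36 | 20.9% | 95.5% | 12 | 5.9% | 83.8% |

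At n = 36 a cut-off of 11 still gives 11.7%, so 12 is needed.

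**Where the two rules disagree.** With 10 CRs at n = 32 to 35, or 10 or 11 CRs at n = 36, the count rejects and the exact test does not. At n = 28 to 31 they agree. At 27 or fewer the count is the stricter of the two: 9 CRs give p = 0.095 at n = 27 and 0.077 at n = 26, yet the count does not reject. That side costs power but does not breach the 10%.

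**How likely this is.** Assume that each of 36 enrolled patients is independently eligible and treated with probability y. The analysed number N is then Binomial(36, y), and the average type I error of the count is Σ P(N = n) × P(X ≥ 10 | n, 0.21). The protocol's planning ratio gives y = 31/36 = 86.1%; the other values show the range.

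| Yield y | P(N ≥ 32) | Average type I error of the count |
|---|---|---|
| 80% | 12.7% | 6.8% |
| 31/36 | 42.7% | 10.2% |
| 90% | 71.1% | 12.7% |
| 95% | 96.8% | 16.6% |

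At 31/36:

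- P(N = 32, 33, 34, 35, 36) = 18.3%, 13.8%, 7.5%, 2.7%, 0.5%.
- P(28 ≤ N ≤ 31) = 51.9% and P(N ≤ 27) = 5.4%.
- Given N ≥ 32, the average type I error is 13.6%.
- Under the null, the count rejects where the exact test does not with probability 2.9%. The reverse has probability 0.3%.

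**The case against.** The strongest reply is that nothing has been miscalculated. The sentence just before the rule sets 31 patients, 12.1.2 and 5.2 both tie the 36 to 31 eligible, treated patients, and 36 is a ceiling that allows for losses. On that reading 10 is simply the exact test's cut-off at 31. A statistician would apply the named test at whatever number is realised, and an analysis plan could say so. The effect is also small on average: 10.2% against 10% at the planning yield, and the 20.9% case has a probability of only 0.5%. Losing power to tidy this up in a single-arm phase II screen may not look worthwhile.

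Much of this stands. The design is correct at 31, enrolment is capped at 36, the problem is conditional on more than 31 being analysed, and the average excess at the planning yield is slight. Three things remain:

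- The protocol did not leave the cut-off to a later document. It printed a count, and the efficacy population in 12.2.2 then supplies a number that need not be 31.
- The average depends on losing about 14% of enrolled patients (5/36). Fewer losses make it worse.
- The trial is read at one realised number. An acceptable average does not settle which rule governs when the two conflict at that number.

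**Conclusion.** The concern holds. The cut-off of 10 is right for 31 patients and for 28 to 30. If 32 to 36 Cohort A patients are eligible and treated, which the text allows, the printed count has a type I error of 11.6% to 20.9% and contradicts the exact 10% test named beside it.

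The per-n figures rest only on the protocol's own rates and the exact binomial distribution. The 43% chance of exceeding 31 and the 10.2% average also rest on 36 patients being enrolled and on independent eligibility at 31/36. Over yields from 80% to 95% the average runs from 6.8% to 16.6%. This should be fixed because it concerns the one remaining efficacy decision and needs only wording. It is not a fault in the sample size calculation.

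**What to change.** Before responses are analysed, adopt one of the following in 12.2.1 and carry it into 12.1.2.1.

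**(a) Tie the cut-off to the realised number.** State that the exact binomial test at one-sided 10% is applied to all eligible, treated Cohort A patients, with cut-offs of 10 for 28 to 31, 11 for 32 to 35 and 12 for 36. For fewer than 28, say whether 10 is kept as conservative or the exact cut-off is used (9 for 24 to 27).

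**(b) Fix the analysed set.** State that the primary test uses the first 31 eligible, treated Cohort A patients in registration order, with the cut-off of 10.

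In either case, say that 86% power and 10% type I error apply at 31 patients.

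The change is wording only; the cost is some power. Averages at the 31/36 yield:

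| Rule | Average type I error | Average power |
|---|---|---|
| Printed count of 10 at every n | 10.2% | 84.6% |
| (a) exact cut-off at every n | 7.5% | 81.9% |
| (a) with 10 kept for all n up to 31 | 7.2% | 81.2% |
| (b) first 31 only | 8.5% | 82.6% |

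Above 31, option (a) has power below 86% at 32 (79.5%), 33 (83.1%) and 36 (83.8%). Option (b) leaves up to 5 eligible, treated patients out of the primary test.

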12.2.2 Secondary Objectives

The secondary objectives for phase I and II of this study will include evaluation of regimen-related toxicities for the combination of ixazomib and ibrutinib in relapsed/refractory MCL; evaluation of the ORR for the drug combination; and to evaluate the median PFS and OS for patients treated with the drug combination.

To describe the ORR for phase I and II, descriptive statistics will be used to compute the proportion of patients who achieved complete and partial response to the drug combination. A 90% exact binomial confidence interval (CI) around the overall response rate estimate from the phase II portion of this study will be computed for descriptive purposes. Based on the planned dose escalation and de-escalation, between 6 and 12 patients will be accrued to the phase I portion of this study.

The median PFS and OS will be evaluated using the Kaplan Meier method, separately for phase I and II patients. The estimates from the phase I will give preliminary information about efficacy which will be further assessed in the phase II patients. The patients included in survival efficacy analysis will include eligible and treated patients only.

All enrolled patients who receive treatment, irrespective of eligibility, will be reviewed for toxicities attributable to treatment. The phase I assessment of treatment-related toxicities of Grade 3 or higher will be described using proportions. In phase II, if 72 patients (up to 36 in each cohort; **August 7, 2020: BTK-pretreated cohort closed.**) are treated and assuming there is an equal rate of toxicity in both cohorts, the maximum width of 90% CI on the proportion of treatment-related grade 3 or higher toxicity in both cohorts, combined, will be no wider than 20%. The probability of observing at least one rare toxicity (true rate of 5%) is approximately 97.5%. **August 7, 2020:** Among 36 treated patients, the maximum 2-sided width of a 90% CI around the proportion of treatment related Grade 3 or higher toxicity will be within 29.4% and the probability of seeing ≥ 1 rare toxicity if such toxicity has a true prevalence of 5% for example is 84.2%.

We will also describe and tabulate all adverse events, regardless of treatment attribution.

To assure an adequate number of eligible, treated patients, up to 36 patients will be enrolled to each arm. This will result in a maximum accrual of 84 patients for the full study (**August 7, 2020: BTK-pretreated cohort closed; updated per Section 12.1.2.1.**)

The efficacy assessment population will include all eligible and treated patients while the adverse events assessment population will include all treated patients, regardless of eligibility.

12.3 Planned Analyses

12.3.1 Toxicity Monitoring Plan

Toxicity and adverse events for all enrolled patients will be monitored throughout the conduct of the study. For the phase I portion of the study, all patients will be evaluated for the development of a DLT as defined in Section 6.2.1. Those patients experiencing a DLT shall be removed from study therapy and the dosing for subsequent cohorts of patients shall be adjusted as described in the protocol.

All other toxicities or adverse events encountered for all patients from the time of study treatment initiation (any toxicities or adverse events related to a protocol-mandated intervention after informed consent is signed will also be included) until the withdrawal of consent or the patient has been off study therapy for 30 days shall be reported, regardless of attribution. We shall review all reported adverse events and shall present recurrent adverse events, grade 3-5 adverse events, or other adverse events felt to be clinically significant and related to study therapy in tabular form.

In addition to the planned tabular description of encountered adverse events, PrECOG shall convene a data safety monitoring board to review the safety of all enrolled patients and ensure compliance with all appropriate guidelines.

12.3.2 Analyses of Correlative Studies

13. Laboratory and Pathology Correlative Studies

13.1 Correlative Studies

13.1.1 Overview

In addition to the planned primary assessments of safety/tolerability and efficacy of the combination, we will also evaluate several candidate predictive and prognostic biomarkers in MCL through analysis of mandatory collected tissue samples, bone marrow aspirates, and peripheral blood. In addition, patient samples collected at pre-specified time points shall be sent to the ECOG-ACRIN Central Biorepository Pathology Facility (E-A CBPF) to be stored and used for future study.

Several of the planned analyses shall take place at the local site under the supervision of the treating investigators while others shall be conducted centrally through the use of the repository.

NOTE: If sufficient bone marrow and tumor tissue are available, submission is mandatory. No bone marrow biopsy/aspirate or tissue biopsy should be performed solely for the purposes of obtaining research samples.

13.1.2 Methodology

Local Assays:

Ki67 Proliferative Index: The Ki67 proliferative index shall be assessed for all tumor samples used to confirm the diagnosis of relapsed MCL for the purposes of this study. This shall be conducted according to each institutional practice and shall be reported as a percentage of cells expressing Ki67. This shall occur at one time point at the time of study entry. Patients for whom there is no tissue available to conduct this assessment will **NOT** require repeat biopsies simply for the purposes of conducting this assessment.

Cytogenetic Analyses: Each site shall submit a bone marrow aspirate sample and/or a tumor tissue sample (nodal or extranodal) for cytogenetic assessments. These assessments shall be conducted locally according to institutional standards. In addition to a conventional cytogenetic assessment, samples shall be assessed by FISH for t(11;14) and FISH for del(17p). Patients shall require 1 (one) sample (either from the bone marrow or from involved tissue) with preference given towards using a sample that is known to be involved with MCL.

Vitamin D Level Assessment: All patients at the time of study enrollment will have a 25(OH) Vitamin D3 level drawn by peripheral blood draw. This one-time assessment will be processed locally.

Centrally Processed Assays:

Peripheral blood and involved tissue samples shall be sent to a central lab for future use. Planned assessments include the following:

PSMB1 Allele Frequency: Given the potential association of the PSMB1 P11A (G allele) with prolonged PFS and OS in patients treated with bortezomib, we will assess the allelic frequency among enrolled patients. All patients will provide a peripheral blood sample at the time of enrollment that will be utilized to evaluate allelic frequency. This shall be determined using a TaqMan SNP assay.

BTK Mutational Analysis: All patients will have a mutational analysis of BTK and PLC-γ2 performed on involved tissue samples. This will be performed using the commercially available NeoGenomics assay and will require Formalin-Fixed, Paraffin-Embedded (FFPE) tissue or bone marrow from aspirate.

Future studies: We will collect and store samples for future correlative studies and will be incorporated into this protocol as future amendments as they are developed.

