Enrollment to Cohort A: BTK-naïve will continue. We plan to reach our original accrual goal of 36 BTK-naïve subjects treated at the established Dose Level 2 for 31 eligible, treated patients. The Phase I BTK-naïve patients treated at Dose Level 2 will be included in the 36 patient total. Seventeen additional BTK-naïve patients will be enrolled to complete this cohort.

Enrollment to Cohort B: BTK-pretreated will close. To date, only two patients have enrolled in Cohort B.

2. Study Objectives

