2.3 Exploratory Objectives

3. Selection of Patients

Each of the criteria in the checklist that follows must be met in order for a patient to be considered eligible for this study. Use the checklist to confirm a patient's eligibility. For each patient, this checklist must be photocopied, completed and maintained in the patient's chart.

In calculating days of tests and measurements, the day a test or measurement is done is considered Day 0. Therefore, if a test is done on a Monday, the Monday four weeks later would be considered Day 28.

PrECOG Patient No. _____

Patient's Initials (F, M, L) _____

Physician Signature and Date _____

NOTE: PrECOG does not allow waivers to any protocol specified criteria. All eligibility criteria listed in Section 3 must be met, without exception. The registration of individuals who do not meet all criteria listed in Section 3 can result in the participant being censored from the analysis of the study, and a major protocol violation. All questions regarding clarification of eligibility criteria must be directed to the Medical Monitor or PrECOG Study Contact.

NOTE: Institutions may use the eligibility checklist as source documentation if it has been reviewed, signed, and dated prior to registration by the treating physician.

_____ 3.1 Patients must have relapsed or refractory, pathologically proven mantle cell lymphoma. Patients must have a current or prior tissue sample that is IHC positive for cyclin D 1 or that is positive by FISH or cytogenetics for t(11;14).

Date of Relapse/Refractory MCL: _____

_____ 3.2 Patients must have been refractory to and/or relapsed/progressed after at least 1 prior therapy.

Date of Last Therapy: _____

_____ 3.3 Prior autologous or allogeneic transplant are allowed. Patients may not have active grade II-IV acute GVHD or moderate/severe chronic GVHD by NIH criteria and may not require immunosuppressive medications and/or corticosteroids for the management of acute or chronic GVHD.

_____ 3.4 **Phase I:** Prior proteasome inhibitor and/or Bruton's tyrosine kinase inhibitors are allowed but patients may not have been exposed to the combination of proteasome inhibitor and BTK inhibitor. Patients who have progressed on ibrutinib that are felt to be at high risk for rapid progression on this study shall not be eligible for the phase I portion of the study.

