- 8 Bone marrow samples will be sent for conventional cytogenetics, FISH for t(11;14) and FISH for del(17p) [conventional cytogenetics, FISH for t(11;14) and FISH for del(17p) may also be done on tumor tissue samples (nodal or extranodal) in lieu of or in addition to bone marrow review].
- 9 Pathologists at the participating site must review available tissue samples to confirm the diagnosis of MCL. If a pathology review has already been completed in the routine care of the patient, then additional review is not required. All patients should have an assessment of Ki67 performed on available tissue. Tissue used for pathology review should ideally be from the time of relapse but pre-treated tissue can be used if that is the only available sample.
- 10 Research samples shall be obtained at the time of screening/study entry, after cycle 3, at time of suspected CR, and at the end of therapy or time of progression. Refer to Section 13 for details.

Screening/Study Entry

Peripheral Blood: Two 6 mL in EDTA tubes

Bone Marrow: One 10 mL in EDTA tube

FFPE: Block preferred or 1 H&E slide plus 10 unstained slides

After Cycle 3 (up to 5 days before Cycle 4, Day 1)

Peripheral Blood: Two 6 mL in EDTA tubes

At time of Suspected CR

Peripheral Blood: Two 6 mL in EDTA tubes

End of Therapy/At Time of Progression (within 45 days of last dose of study medication)

Peripheral Blood: Two 6 mL in EDTA tubes

NOTE: If sufficient bone marrow and tumor tissue are available, submission is mandatory). No bone marrow biopsy/aspirate or tissue biopsy should be performed solely for the purposes of obtaining research samples.

- 11 Patients will receive ixazomib orally on days 1, 8, and 15 of each 28 day cycle (1 cycle=28 days) [Section 6.1.1 for dosing administration]. Ixazomib shall be administered in the clinic on Cycle 1, Day 1 and Cycle 1, Day 15 (Day 8 can be administered at home). For subsequent cycles, ixazomib doses on Days 8 and 15 can be administered at home. Ixazomib Medication Diary will be reviewed for compliance and collected every cycle after Cycle 1 (Appendix III). Ibrutinib shall be administered orally daily on days 1-28 [Section 6.1.2 for dosing administration]. Ibrutinib Medication Diary will be reviewed for compliance and collected every cycle (Appendix IV). See Section 6.2 for Phase I and Section 6.3 for Phase II dosing instructions and Section 6.5 for dose delays/modifications.

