13.1.4.3 Peripheral Blood Samples

Sites should submit peripheral blood samples in EDTA tubes as noted in Section 13.1.3.

EDTA Tube Processing for Plasma and Buffy Coat****Process sample within 30 minutes of collection****

- Gently mix blood sample by inversion 10 times (do not shake).
- Place tube immediately on wet ice for 5 minutes.
- Centrifuge at 1200 RPM for 15 minutes at 4°C . If a refrigerated centrifuge is not available, spin sample at room temperature (1200 RPM for 15 minutes). Immediately place the tube on wet ice after centrifugation.

After centrifugation, the plasma layer will be at the top half of the tube. The nucleated cells (WBC) will be in a whitish layer, called the “buffy coat”, just under the plasma and above the red blood cells.

Plasma Preparation:

- Using a transfer pipette take the top two-thirds of the plasma and transfer plasma into a 15 ml conical centrifuge tube, be careful not to disturb the buffy coat layer in the EDTA tube (**NOTE:** see below for buffy coat processing instructions). Centrifuge the 15 ml conical tube at 1200 RPM for 15 minutes at 4°C . If a refrigerated centrifuge is not available, spin sample at room temperature (1200 RPM for 15 minutes). Immediately place the conical tube on wet ice after centrifugation.
- Transfer equal amounts of plasma into two (2) properly labeled polypropylene tubes for cryopreservation being careful not to disturb the small PBMC/pellet.
- Store the two aliquots of plasma samples in the freezer at $\leq -70^{\circ}\text{C}$ or colder until they are shipped to central lab.

Buffy Coat Preparation:

- From the EDTA tube remove and aliquot the “buffy coat”; be careful not to disturb the layer of red blood cells.
- Store the aliquot of cells in two (2) properly labeled polypropylene tube for cryopreservation.
- Store the sample in the freezer at $\leq -70^{\circ}\text{C}$ or colder until it is shipped to central lab.

Plasma and buffy coat samples should be batched together and shipped approximately every 4 months. Individual patients should only be included in the shipment if all of their samples have been completed. Samples should be shipped **Monday-Thursday**. Samples must be shipped on dry ice via overnight courier.

14. Administrative

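### PSMB1 is genotyped from blood in every patient, although allogeneic transplant recipients are eligible and their blood does not give a valid recipient genotype

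*Protocol*

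**What the plan says.** Three places in the protocol bear on this.

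- **Eligibility, criterion 3.3:** "Prior autologous or allogeneic transplant are allowed". The limits that follow concern active graft-versus-host disease and its treatment. A patient with a functioning donor graft and no such problem can enrol.
- **PSMB1 assay, Section 13.1.2:** citing a potential link with "prolonged PFS and OS in patients treated with bortezomib, we will assess the allelic frequency among enrolled patients". The source is fixed for everyone: "All patients will provide a peripheral blood sample at the time of enrollment that will be utilized to evaluate allelic frequency". The method follows: "This shall be determined using a TaqMan SNP assay".
- **Blood processing, Section 13.1.4.3:** the tubes are split into plasma and buffy coat. On the latter: "The nucleated cells (WBC) will be in a whitish layer, called the “buffy coat”, just under the plasma and above the red blood cells". Sites are told: "From the EDTA tube remove and aliquot the “buffy coat”; be careful not to disturb the layer of red blood cells".

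Section 13.1.1 says that the correlative work evaluates candidate markers of prediction and prognosis. Tumour tissue is also requested at entry (Section 10, footnote 10): "FFPE: Block preferred or 1 H&E slide plus 10 unstained slides". It is mandatory only if enough is available, and 13.1.2 assigns involved tissue to BTK and PLC-γ2 mutation testing, not to PSMB1.

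**The concern.** A SNP assay on blood is a sound way to read a patient's inherited genotype as long as the blood cells are the patient's own. After allogeneic engraftment they are not, or not entirely. The assay would still return a plausible call, so nothing in the result would flag the problem.

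At stake is the pairing of genotype with patient. If PSMB1 is later related to response, progression-free survival or overall survival, a donor's genotype would be set against a recipient's outcome. In a study of this size even one or two misassigned patients matter to a genotype subgroup. A later analysis plan can drop such patients, but it cannot recover their genotype from the wrong cells. Autologous recipients are not affected.

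**Working it through.** **Reading the rules together.** Criterion 3.3 lets allogeneic recipients in. Section 13.1.2 applies blood genotyping to all patients. Section 13.1.4.3 yields one stored fraction that holds the nucleated cells, the buffy coat. Followed as written, the rules genotype allogeneic recipients from donor or mixed leukocyte DNA. The protocol states no figure for this assay, so there is none to reproduce.

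**Inputs for scale**
- Number of allogeneic recipients: not given. Assumed 0 to 3.
- Minor-allele frequency q: not given. Assumed 0.1 to 0.5.
- Donor type and chimerism: not given. Assumed unrelated donor and full donor chimerism; siblings are shown for comparison.
- Denominator: Section 1.5.2 plans "We plan to reach our original accrual goal of 36 BTK-naïve subjects treated at the established Dose Level 2 for 31 eligible, treated patients". The assay covers all enrolled patients, however. From Sections 1.5.2 and 12.1.2.1 that is 12 in Phase I, plus 36 − 6 = 30 further in Cohort A, plus 2 in Cohort B, or 44.

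**Chance that donor and patient differ.** Under Hardy-Weinberg the genotype frequencies are g = (1−q)², 2q(1−q), q². For an unrelated donor, P(differ) = 1 − Σg².
- q = 0.1: 1 − (0.81² + 0.18² + 0.01²) = 1 − 0.6886 = 0.311
- q = 0.5: 1 − (0.25² + 0.50² + 0.25²) = 1 − 0.375 = 0.625

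For a full sibling, P(differ) = 1 − [¼Σg² + ½s + ¼], where s = (1−q)³ + q(1−q) + q³.
- q = 0.1: s = 0.82, giving 1 − (0.172 + 0.410 + 0.25) = 0.168
- q = 0.5: s = 0.50, giving 1 − (0.094 + 0.250 + 0.25) = 0.406

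**Expected wrong genotypes**

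| Recipients | Unrelated donor, q = 0.1 to 0.5 | Sibling donor, q = 0.1 to 0.5 |
|---|---|---|
| 0 | 0 | 0 |
| 1 | 0.3 to 0.6 | 0.2 to 0.4 |
| 3 | 0.9 to 1.9 | 0.5 to 1.2 |

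**Pooled allele frequency.** If a share w of the genotypes are donors', the expected bias is w × (donor-population frequency − patient-population frequency). Three recipients give w = 3/44 = 0.07, or 3/31 = 0.10 if only the eligible, treated Cohort A patients are counted. If donors come from a similar population the second factor is near zero, and so is the bias.

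**The case against.** Several objections have force.

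- **The stated target is a frequency.** Section 13.1.2 commits only to describing the allele frequency. Survival appears there as the reason for choosing the marker. A reader might infer that a planned outcome analysis is corrupted, but no such analysis is visible in the protocol. The harm to outcome analyses is therefore conditional. It is not idle, because Section 13.1.1 gives prediction and prognosis as the purpose of the correlative work.
- **The plan may deal with this elsewhere.** Sections 2.3 and 12.3.2 show headings only in the copy at hand. Section 4.4 refers to a lab manual and 13.1.3 to kit instructions, neither of which is shown. It cannot be said that the plan has no exception anywhere. It can be said that 13.1.2, which fixes the source, applies it to all patients without one.
- **Donor genotype in every case is too strong.** A reader might infer that the assay always reads the donor in these patients. With mixed chimerism or circulating lymphoma cells it would read a mixture. That is still not a valid recipient genotype. Use of the buffy coat is also an inference, since 13.1.2 does not name the blood fraction.
- **The size rests on assumptions.** This stands. The figure of about 2 is the extreme corner: three recipients, unrelated donors, q = 0.5 and full donor chimerism.
- **Tumour tissue is not a clean substitute.** This stands too. Submission depends on availability, a post-transplant block can contain donor leukocytes, tumour DNA can show allelic loss, and the tissue is wanted for mutation testing.

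**Conclusion.** The point holds in a limited form. Sections 3.3 and 13.1.2 together prescribe a sample that does not give a valid PSMB1 genotype in allogeneic recipients. The rule as stated gives a wrong result in these patients, so this is more than a detail left for later.

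The effect is small: somewhere between none and about 2 wrong genotypes under the assumptions above, and fewer with sibling donors. A reader might infer that the reported allele frequency is materially distorted. The documents do not support that, since the frequency would shift only if donors and patients come from populations with different frequencies, and then only by the small share affected. The consequence that matters is misclassification if PSMB1 is related to outcome. The primary complete response endpoint, its sample size and its decision rule are untouched. Lowest severity.

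**What to change.** Add to Section 13.1.2 that patients with a prior allogeneic transplant are excluded from the PSMB1 allele-frequency analysis and from any analysis of PSMB1 against outcome, and that their number is reported. They can be identified from the medical and surgical history already taken at screening (Section 10), so no new procedure is needed.

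If the sponsor wishes to keep these patients in view, genotype from submitted fixed tumour tissue can serve as a sensitivity analysis only, because of possible donor cells and allelic loss.

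The cost is a sentence or two of text. The downside is that a few patients, possibly none, will have no usable PSMB1 genotype.
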